3 METHODS

The sample used will be the stool sample at the diagnosis (or, failing that, the one made before the 3rd injection of durvalumab). An analysis of its composition will be performed by metagenomics to establish the composition of the intestinal microbiota of the patient before treatment.

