2 Must be contrast enhanced CT scan; low dose surveillance CT is not acceptable. To ensure comparability, the baseline scans and subsequent scans to assess response must be performed using identical techniques (i.e. scans performed immediately following bolus contrast administration using a standard volume of contrast, the identical contrast agent, and preferably the same scanner). CT appearance consistent with post-operative change is expected and does not preclude inclusion.

3 MUGA or ECHO, only for patients with significant cardiac history.

4 Serum, plasma and feces for correlatives must be taken after consent is obtained but prior to day 1 dosing of cycle 1 - may be done after inclusion providing it is done prior to day 1 dosing or within 14 days prior to inclusion.

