13.3.2 Feces

Feces will be collected before first infusion of durvalumab.

Currently, only few parameters have been identified as predictive biomarker of response, such as positive expression of PD-L1, and high mutational loads of tumors that appears to be associated with a higher response rate to anti-PD1 mAb. New lines of evidence demonstrated the biological significance of the gut microbiome (diverse range of symbiotic microorganisms) has an important contributor of pulmonary pathologies such as asthma and COPD (see APPENDIX V).

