1 BACKGROUND AND PROJECT AIMS

Prospective collection of stool samples from patients enrolled in the Ionesco study before the instauration of immunotherapy treatment to perform metagenomic analyses in order to (i) compare fecal dysbiosis in NSCLC patients at the diagnosis with matched healthy volunteers from the MetaHIT study results, (ii) identify metagenomics signatures that predict treatment response/resistance and immune related toxicities and (iii) correlate gut microbiome composition with data obtained in the Immune atlas part.

Anti-PD1/anti-PD-L1 mAbs represents a major paradigm shift in cancer therapy. However, despite the unprecedented efficacy of these innovative and treatments determination of novel biomarker is of paramount interest.

Currently, only few parameters have been identified as predictive biomarker of response, such as positive expression of PD-L1, and high mutational loads of tumors that appears to be associated with a higher response rate to anti-PD1 mAb. New lines of evidence demonstrated the biological significance of the gut microbiome (diverse range of symbiotic microorganisms) has an important contributor of pulmonary pathologies such as asthma and COPD (1). The gut-lung axis interaction plays a key role in immune set tone and ultimately could be an important factor in lung cancer carcinogenesis and further studies are warranted.

Beyond the direct interactions between host immune system and microbiome, an additional layer of complexity exists associated to cancer therapies.

Our group and co-investigators have paved the way by demonstrating the pivotal role of microbiome on cyclophosphamide (CTX) and platinum based chemotherapy (2,3). We have extended these findings to immune checkpoint blockade (ICB) by the anti-CTLA4 Ab (Ipilimumab) and identified *Bacteroides* spp. responsible for IL-12 production increasing systemic Th1, which improves anti-CTLA response in mice (4). Recently, three independent groups, including ours, highlighted that gut microbiome composition at baseline predicts response to PD1/PDL1 blockade in RCC, NSCLC and melanoma (5-7). Furthermore, the cause effect-relationship between gut commensals and treatment response was demonstrated using, avator murine model. Oral gavage of dysbiotic mice with immunogenic bacteria enriched in responder patients restored anti-PD1 anti-cancer activity.

In this study we plan to collect samples at baseline.

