4 RESSOURCES REQUIRED FOR THIS ANCILLARY STUDY

The collection kit (provided by gustave roussy cancer campus) is given to the patient at the screening visit. Patients bring back their sample at the hospital the day of the first administration of immunotherapy. This corresponds to a single sample, collected at baseline, prior immunotherapy.

According to our previous data, if the baseline sample couldn't have been collected, it is possible to collect feces until before the 3rd administration of durvalumab, without observing significant variation of the gut microbiome.

Depending on the center location, two protocols of collection are available.

In ile de france fresh samples are transferred from the centre to grcc by a courier. Samples are aliquoted and stored at -80° c at grcc (procedure).

Outside of ile de france, patient aliquots themselves their samples in tubes containing a stabilization solution. Samples are stored on site at -80° c (procedure bis).

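### Appendix V, part C lets a stool sample taken after up to two infusions stand for the pre-treatment microbiome, against the pre-dose rule in Sections 7 and 14.3 (minor; exploratory objective only)

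*Protocol*

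**What the plan says.** The body of the protocol gives one rule without exception. Section 7 (Pre-treatment evaluation), footnote 4: "Serum, plasma and feces for correlatives must be taken after consent is obtained but prior to day 1 dosing of cycle 1". The feces paragraph within Section 14.3 (printed as 13.3.2): "Feces will be collected before first infusion of durvalumab".

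Appendix V, part C (gut microbiome) starts from the same rule. Its aims section says "In this study we plan to collect samples at baseline", and its resources section says "This corresponds to a single sample, collected at baseline, prior immunotherapy".

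Its Methods then allow a substitute: "The sample used will be the stool sample at the diagnosis (or, failing that, the one made before the 3rd injection of durvalumab". The purpose of the analysis, whichever sample is used, is "to establish the composition of the intestinal microbiota of the patient before treatment". The resources section limits the substitute to patients whose baseline sample could not be obtained. Citing the group's previous data, it says that "it is possible to collect feces until before the 3rd administration of durvalumab, without observing significant variation of the gut microbiome".

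The results serve several aims. One is to compare dysbiosis at diagnosis with matched healthy volunteers. Another is to "identify metagenomics signatures that predict treatment response/resistance and immune related toxicities".

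**The concern.** A baseline predictor should be fixed before the outcome can occur. If it may be measured later, the event, or the treatment given for it, can change the marker, and the analysis would then read a consequence as a predictor. Stool is exposed to this. Gut toxicity is among the toxicities of interest: colitis is listed as an adverse event of special interest in Section 12.1.1. The management options for diarrhoea and colitis in Appendix II include probiotics, steroids and prophylactic antibiotics, and Section 8.8.2 lists antibiotics as permitted supportive care.

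There is also a practical problem. A site following Section 7 and a site following Appendix V would handle a missed baseline sample differently, and the analyst would receive both kinds of sample under one label.

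**Working it through.** The protocol states no figure for this point, so the check sets the timing rules side by side and adds the schedule arithmetic.

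**1. When the sample may be taken**

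| Place | Latest permitted time |
|---|---|
| Section 7, table and footnote 4 | before day 1 dosing of cycle 1 |
| Section 14.3, feces paragraph | before the first infusion |
| Appendix V, part C, 1 (aims) | baseline |
| Appendix V, part C, 4 (resources), main rule | baseline, before immunotherapy |
| Appendix V, part C, 3 (Methods) and 4, fallback | before the third infusion |

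The first four agree and the fallback does not. The Appendix I flow sheet does not settle the matter, since its correlative-sample row names only serum and plasma.

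**2. How late a fallback sample can be**

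The Section 4 schema puts infusions on days 1, 15 and 29; Section 8.1 gives weeks 0, 2 and 4, which is the same schedule.
- Latest delay after the first dose: 29 − 1 = 28 days.
- Doses already given by then: 2 of 3, or 67% of the planned infusions.

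**3. Overlap with the toxicity outcome**

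Section 11.1.3 makes patients evaluable for toxicity from their first treatment. The outcome window therefore opens on day 1, and up to 28 days of it can precede the sample.

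**4. Overlap with the response outcome**

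Section 10.1 places the second CT and PET after durvalumab and before surgery, and pathological response is read on the surgical specimen (Section 11.1.2). On the planned schedule a fallback sample still comes before any response assessment.

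**5. Comparison with healthy volunteers**

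This comparison is meant to describe patients at diagnosis. A sample taken after one or two doses does not have that status, whatever its composition.

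**6. Size**

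The bias depends on the share of patients using the fallback and on how many of them had gut toxicity or a relevant drug before sampling. The protocol gives neither, so no bias can be calculated.

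**The case against.** The fallback is a conditional exception. The kit is handed out at screening and returned on the day of the first infusion, and the later sample is allowed only if that fails. The feces paragraph in Section 14.3 refers the reader to Appendix V. The protocol also gives a reason for the exception. All of this stands, and it limits the problem to a subset of patients. It does not make a sample taken after dosing a pre-treatment one. The reason comes without figures or a reference. The earlier data may have included patients with gut toxicity, antibiotics, probiotics or steroids; the protocol does not say, so neither coverage nor lack of it can be asserted.

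Four stronger readings are tempting and are not supported:

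- **That the treatment-related diarrhoea rate of 7.3% in Section 2.1 measures the problem.** It comes from 694 patients with advanced solid tumours and is not limited to the first 28 days. Applied to 81 patients it gives 0.073 × 81 = 5.9 cases. If 5% to 20% of patients used the fallback (an assumption), independently of diarrhoea, that would be 5.9 × 0.05 = 0.3 to 5.9 × 0.20 = 1.2 patients, before removing diarrhoea that starts after sampling. A link between lateness and toxicity would raise this, but nothing in the protocol shows one.
- **That response is affected by the same reversal of order.** Response is assessed after any fallback sample, so the ordering problem concerns toxicity.
- **That patients with late samples differ systematically from the rest.** This is possible but speculative, and leaving them out would not remove such a selection.
- **That the toxicity aim is mainly about gut events.** It covers immune-related toxicities in general, and the events named for analysis in Section 15.5 are pulmonary, endocrine, dermatologic and hepatic.

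It is also fair to say that sensitivity analyses for an ancillary study often sit in a separate analysis plan. The issue here is a stated rule and a stated label that conflict with other stated rules.

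**Conclusion.** The point holds in a limited form. Two body sections require stool before dosing. Appendix V, part C accepts, when the baseline sample is missing, one taken up to 28 days and 2 of 3 infusions later, and treats it as pre-treatment. For immune-related toxicity the predictor can then be measured after the outcome window has opened. For the healthy-volunteer comparison the sample is mislabelled. Reverse causation is a plausible risk, not a demonstrated one, and its size cannot be given because the share of late samples is unknown.

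The microbiome analysis is an exploratory objective (Section 3.3). The primary endpoint, sample size, decision rule and safety monitoring are untouched. Severity: minor. The conclusion assumes that the planned infusion days are kept and that the fallback is used as written.

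**What to change.** Reconcile Section 7, the feces paragraph of Section 14.3 and Appendix V, part C, so that any exception is stated the same way in all three. In Appendix V:

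- base the main predictive analyses and the healthy-volunteer comparison on samples taken before the first infusion;
- record the sampling date relative to each infusion;
- label later samples as on-treatment and use them only in a sensitivity analysis that takes account of earlier diarrhoea and of antibiotic, probiotic or steroid use.

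The information for that adjustment should already be available: Section 9.1 has concomitant medication recorded before each infusion and adverse events evaluated after each cycle.

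The change is to wording, and no sample need be discarded. The main exploratory analysis loses a few patients, and any selection among those without a baseline sample remains, so their number should be reported.

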4 RESSOURCES REQUIRED FOR THIS ANCILLARY STUDY

The collection kit (provided by gustave roussy cancer campus) is given to the patient at the screening visit. Patients bring back their sample at the hospital the day of the first administration of immunotherapy. This corresponds to a single sample, collected at baseline, prior immunotherapy.

According to our previous data, if the baseline sample couldn't have been collected, it is possible to collect feces until before the 3rd administration of durvalumab, without observing significant variation of the gut microbiome.

Depending on the center location, two protocols of collection are available.

In ile de france fresh samples are transferred from the centre to grcc by a courier. Samples are aliquoted and stored at -80° c at grcc (procedure).

Outside of ile de france, patient aliquots themselves their samples in tubes containing a stabilization solution. Samples are stored on site at -80° c (procedure bis).

5 ORIGINALITY OF THIS STUDY

This project offers a unique opportunity to study the role of the gut microbiota in predicting the neoadjuvant response to durvalumab in lung cancer and to study the covariation of its composition with the intraluminal immune environment post-treatment.

APPENDIX VI - DURVALUMAB DOSE CALCULATION FOR SUBJECT WITH WEIGHT < 30 kg

The durvalumab dosing should be done depending on subject weight (if subject is < 30kg):

1. Cohort dose: X mg/kg
2. Subject weight: Y kg
3. Dose for subject: XY mg = X (mg/kg) × Y (kg)
4. Dose to be added into infusion bag:

$$\text{Dose (mL)} = \text{XY mg} / 50 \text{ (mg/mL)}$$

where 50 mg/mL is durvalumab nominal concentration

The corresponding volume of durvalumab should be rounded to the nearest tenth mL (0.1 mL). Dose adjustments for each cycle only needed for greater than 10% change in weight.

5. The theoretical number of vials required for dose preparation is the next greatest whole number of vials from the following formula:

$$\text{Number of vials} = \text{Dose (mL)} / 10 \text{ (mL/vial)}$$

Example:

1. Cohort dose: 10 mg/kg
2. Subject weight: 30 kg
3. Dose for subject: 300 mg = 10 (mg/kg) × 30 (kg)
4. Dose to be added into infusion bag:

$$\text{Dose (mL)} = 300 \text{ mg} / 50 \text{ (mg/mL)} = 6.0 \text{ mL}$$

5. The theoretical number of vials required for dose preparation:

$$\text{Number of vials} = 6.0 \text{ (mL)} / 10.0 \text{ (mL/vial)} = 1 \text{ vials}$$
